Our initial sample size was justified based on the feasibility outcome of compliance with PMR among patients in the RELAX group. We anticipated an initial compliance rate of at least 75%. The planned sample size also provided adequate power for the primary exploratory outcome (\square MIDAS from baseline to 3 months) and the secondary outcome (number of headaches/30 days). Considering \square MIDAS as the primary outcome can reduce data skewedness and improve study power. Based on the study, the standard deviation (SD) of \square MIDAS ranges from 5 to 7. Using the conservative estimate of SD=7, group sample sizes of 30, with anticipated 25% dropout leading to approximately 23 patients per group, achieve 80% power to detect a clinically significant difference of 5.75 between the groups, assuming a significance level of 0.05 using a two-sided two-sample t-test.

Subsequently, based on later data, we found that only about half of the participants have full follow-through so the 90 (similar to the NIH request) is more adequate for this.

GenderofSubjects

Both genders will be included.

AgeofSubjects

18-80 (18 – 65 in urgent care)

Racialand Ethnic Origin No enrollment restrictions.

Inclusion Criteria [Box1] age 18-80;(18-65 in urgent care)

Meets migraine criteria based on International Classification of Headache Disorders (ICHD) 3 beta (based on questions in REDCap), Migraine Disability Assessment (MIDAS) score >5. 4+ headache days a month.

OR

Meets Chronic PTH criteria based on International Classification of Headache Disorders (ICHD) 3 beta (based on questions in REDCap) and had 4+ headache days a month, is 3-12 months post initial injury.

OR

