Disability is a commonly used outcome in migraine trials evaluating outcomes of acute and preventative interventions, ^{36,37} because it is easy to understand and is meaningful to patients.

TABLE 2: OUTCOME MEASURES: DEFINITIONS AND SCALES

Aim 1: FEASIBILITY AND ACCEPTABILITY OUTCOMES

Feasibility: a) Proportion of patients who enrolled in the study/were recruited for the study, b) Percentage of patients who did PMR ≥4/7 days of the week, c) Number of days spent doing PMR ≥5 minutes/day as determined with the backend analytics in the RELAXaHEAD app, d) Minutes/day spent doing PMR, e) Reasons for non-adherence

Acceptability: a) Satisfaction using Likert scale questions on RELAXaHEAD usability, content, and functionality b) Willingness to repeat a similar treatment intervention in the future (Definitely No/Probably No/Unsure/Probably Yes/ Definitely Yes) c) Attrition

Aim 2: MIGRAINE QUALITY OF LIFE AND MIGRAINE DISABILITY OUTCOMES

Primary Outcome = Functionality: □□MIDAS: difference between scores of MIDAS ^{32,38} at 3 months and baseline. MOS Pain Effects Scale (PES).

Pain: 50% decrease in frequency and/or intensity of HAs (measured by electronic HA diary data).³⁹ Will control for adherence with PMR. (*Frequency*: # of HA days/30 days starting and ending at midnight; *Intensity*:0 (no HA), 1 (mild HA), 2 (moderate HA), 3 (severe HA) recommended by IHS.³⁹

Acute medications used*: As recommended by IHS:# of days/week treated with medications, # of drug administrations/week for medications. Medications included: NSAIDs, acetaminophen, caffeine, aspirin, triptans, barbiturates, opioids, antipsychotics.

Psychiatric Comorbidity, Stress Levels, and Sleep: PROMIS depression and anxiety screens, the Perceived Stress Scale, 42-44 and Sleep Duration and Quality using Likert Scale questions (How would you rate the quality of your sleep/How rested or refreshed did you feel when you woke-up for the day). 45

Adverse Events: *PMR*: Paradoxical anxiety, time burden/inconvenience, and any other adverse events experienced. Recorded in real time in the study diary.³⁹ As recommended by the IHS: Adverse events will be recorded as follows: Event Severity: Mild, Moderate, Severe; Event Seriousness: Serious, Non-Serious, Start and End Time.³⁹

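### The plan's only between-arm method is an unadjusted t-test on MIDAS change; ANCOVA on baseline should be prespecified, for a power gain that may be small

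*Combined protocol and SAP*

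**What the plan says.** The Phase 2 sizing text (under Study Design) takes the change in MIDAS from baseline to 3 months as the primary exploratory outcome, on the ground that it "can reduce data skewedness and improve study power". It says the SD of that change "ranges from 5 to 7" and plans on the upper value. The test it names is an unadjusted t-test of the two arms, two-sided at the 5% level. After allowing for a quarter of each arm of 30 dropping out, it claims that the remaining numbers "achieve 80% power to detect a clinically significant difference of 5.75 between the groups". A later paragraph reports that "only about half of the participants have full follow-through" and treats 90 patients as the better number.

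Table 2 defines the Aim 2 primary outcome as the "difference between scores of MIDAS", 3-month against baseline. The Analysis Plan text before that table makes change in MSQv2 primary. The Aim 2 statement names both MSQ and MIDAS and describes within-group analyses. No section names a between-arm model or a baseline covariate.

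Methods & Procedures has patients randomised after consent, with baseline data collected afterwards. MIDAS above 5 is also an entry criterion for migraine patients.

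**The concern.** This is a randomised two-arm phase sized on a between-arm difference, yet the analysis text does not say how the arms will be compared. The unadjusted t-test in the sizing paragraph is the only candidate. If it becomes the analysis by default, the trial uses the baseline score inefficiently. Subtracting baseline fixes its coefficient at 1, whereas ANCOVA estimates the coefficient from the data.

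Precision is at stake in a comparison with about 23 evaluable patients per arm and no margin over the power target. Leaving the model open also allows it to be chosen after the data are seen.

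**Working it through.** **Inputs from the sizing text:** SD of change 7, difference 5.75, two-sided alpha 0.05, 30 per group, 25% dropout, later follow-through of about half, and 90 patients in Phase 2. **Assumed:** 1:1 allocation, equal MIDAS variance (σ²) at both visits, and a baseline to 3-month correlation ρ, which the documents do not give and which is therefore varied.

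**1. The plan's own figure.** Evaluable per arm: 30 × 0.75 = 22.5, taken as 23. The standard error is 7 × √(2/23) = 2.064, and 5.75/2.064 = 2.786. Normal approximation: Φ(2.786 − 1.960) = 79.5%, so the stated 80% reproduces. The exact t-test (noncentral t, 44 df) gives 77.8%. With 90 randomised and half followed, 45 × 0.5 = 22.5 per arm remain and the exact t-test gives 76.8%. The shortfall against 80% is about 2 to 3 points.

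**2. Precision of the two analyses.** Per patient, Var(change) = 2σ²(1 − ρ) and Var(ANCOVA) = σ²(1 − ρ²), a ratio of (1 + ρ)/2. If the baseline and 3-month SDs differ (σ₀, σ₁), Var(change) − Var(ANCOVA) = (σ₀ − ρσ₁)², which is never negative.

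**3. Power.** Holding the change SD at 7, the ANCOVA SD is 7 × √((1 + ρ)/2). Power is from the noncentral t with 2n − 3 df. The last column is the between-patient MIDAS SD that each ρ implies, σ = 7/√(2(1 − ρ)).

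| Analysis | SD | 23 per arm | 22.5 per arm | 15 per arm | Implied σ |
|---|---|---|---|---|---|
| t-test on change | 7.00 | 77.8% | 76.8% | 58.4% | – |
| ANCOVA, ρ = 0.3 | 5.64 | 92.2% | 91.6% | 76.7% | 5.9 |
| ANCOVA, ρ = 0.5 | 6.06 | 88.2% | 87.5% | 70.7% | 7.0 |
| ANCOVA, ρ = 0.7 | 6.45 | 84.0% | 83.1% | 65.3% | 9.0 |
| ANCOVA, ρ = 0.8 | 6.64 | 81.9% | 81.0% | 62.8% | 11.1 |
| ANCOVA, ρ = 0.9 | 6.82 | 79.8% | 78.9% | 60.5% | 15.7 |

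The 15 per arm column is half of the initial 30 per group. There ANCOVA reaches 80% only if ρ is about 0.20 or lower.

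**4. Where ρ is likely to lie.** With the change SD fixed at 7, ρ = 1 − 49/(2σ²). Entry has no upper MIDAS limit, so σ may be large. The documents do not give σ. For assumed values of 12, 15, 20 and 25, ρ is 0.83, 0.89, 0.94 and 0.96, and ANCOVA power at 23 per arm is 81.2%, 80.0%, 79.0% and 78.5%. The gain over 77.8% is then about 1 to 3 points.

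**5. Cost of estimating the slope.** At 23 per arm this multiplies the variance by about 1 + 1/42 = 1.024. Power becomes 91.6%, 87.4%, 83.1% and 78.8% at ρ of 0.3, 0.5, 0.7 and 0.9. Beyond ρ of about 0.95 the change score is level or slightly ahead.

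**6. The plan's power sentence.** Change has lower variance than the raw 3-month score when 2(1 − ρ) < 1, that is ρ > 0.5. With a change SD of 7, this means σ > 7. At an assumed σ of 10, the raw score has 48% power against 77.8% for change.

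**The case against.** The strongest reply is that the t-test is a sizing assumption, not a declared analysis. It appears only in the power statement, in a feasibility trial whose Aim 2 text plans within-group analyses and whose Analysis Plan makes MSQv2 change primary. That stands. A reader might infer that the t-test is the prespecified primary analysis, and the documents do not go that far. The gap is that no between-arm model is specified, so settling the primary outcome and contrast comes first.

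Second, a reader might infer that ANCOVA restores power the trial is missing. The documents report no deficit, the 80% reproduces by normal approximation, and N was set at 90 in view of poor follow-through. The large gains need a low ρ, and at a change SD of 7 that means patients who differ little in MIDAS. The plan also credits MIDAS with excellent test-retest reliability. That is not a 3-month correlation under treatment, but it does not point to a low one.

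Third, a reader might conclude that the power sentence is wrong and should go. It names no comparator. Read as change versus raw score, it holds whenever ρ exceeds 0.5.

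Fourth, chance baseline imbalance does not bias a randomised change-score comparison in expectation. It is a loss of precision already counted in the variance ratio, not a separate harm.

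What survives is that the between-arm analysis is unspecified, the only method mentioned ignores baseline, and adjustment uses data the change score already requires.

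**Conclusion.** The point holds as a recommendation to specify and adjust the between-arm analysis. At 23 per arm the gain over the exact t-test runs from about 14 points (ρ = 0.3) to about 2 points (ρ = 0.9), before the small cost of estimating the slope. It is likely to be at the small end if MIDAS varies widely between patients. These figures rest on the plan's change SD of 7, equal variances at both visits, 1:1 allocation and an assumed ρ.

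The documents do not support the stronger reading that adjustment repairs the trial's power. It does not generally make up for half the patients being lost from an initial 60, and it does not remove bias from missing 3-month scores.

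**What to change.** - Settle which of MIDAS and MSQv2 is primary, and state that the contrast is between arms.
- Prespecify ANCOVA of the 3-month score on arm with the baseline score as covariate, for MIDAS and likewise for MSQv2.
- Use a score recorded before allocation where available. The MIDAS used for eligibility may serve if it is retained. Otherwise, say that baseline was collected after randomisation.
- Check residual skew, and confine log(MIDAS + 1) or rank-based analyses to sensitivity. A log scale changes the estimand, so neither the 5.75-point target nor the power figures carry over.
- State the assumed correlation and its source, with a range.
- Qualify the power sentence as change compared with the raw 3-month score.
- Address missing 3-month scores separately. The rule counting dropouts as non-compliant concerns adherence, not MIDAS.

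For MIDAS the cost is mainly SAP wording, since the change score already requires a baseline. Where no pre-allocation score exists, the order of baseline collection and randomisation also needs attention for patients still to be enrolled.

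### The stated 80% power for a 5.75-point MIDAS difference is a normal-approximation figure; the named t-test gives about 77–78%, and no power is given for the current 90 subjects

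*Combined protocol and SAP*

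**What the plan says.** The calculation is in the combined protocol and SAP, under Study Design, in the sample-size text for Phase 2. It first says that the initial size was justified by compliance with PMR, then adds that it also powers change in MIDAS from baseline to 3 months, called the primary exploratory outcome. The inputs are:

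- SD of the change: "MIDAS ranges from 5 to 7", with the top of the range chosen: "Using the conservative estimate of SD=7".
- Numbers: "group sample sizes of 30, with anticipated 25% dropout leading to approximately 23 patients per group".
- Test: "assuming a significance level of 0.05 using a two-sided two-sample t-test".
- Result: "leading to approximately 23 patients per group, achieve 80% power to detect a clinically significant difference of 5.75 between the groups".

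The next paragraph, still before the eligibility criteria, reports later experience: "only about half of the participants have full follow-through so the 90 (similar to the NIH request) is more adequate for this". It gives no new power figure. The same section says that the 90 came partly from the initial power analysis and partly from a funder request to raise the number.

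**The concern.** Every input needed to check the 80% is stated, and the claim is tied to a named test. At group sizes in the low twenties, the t-test and the normal approximation differ by about two percentage points of power, so a figure from one should not be attributed to the other. Rounding 22.5 completers up to 23 adds a little in the same favourable direction.

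The second gap concerns the trial as it now stands. The 25% dropout assumption has been overtaken by later data and the number has changed, but the only between-group power statement with numbers still describes 30 per group. A reader cannot tell what power the 90 are meant to give for MIDAS change, which Table 2 lists as the Aim 2 primary outcome.

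**Working it through.** **Inputs.** Difference 5.75, SD 7, two-sided alpha 0.05, 30 enrolled per group and 25% dropout, all from the Phase 2 sample-size text. Completers: 30 × 0.75 = 22.5, which the plan rounds to about 23.

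**Formulas.** With n completers per group, SE = 7 × √(2/n) and λ = 5.75 / SE.
- Normal approximation: power ≈ Φ(λ − 1.960).
- t-test: power = P(|T| > t(0.975, 2n − 2)), where T is noncentral t with 2n − 2 degrees of freedom and noncentrality λ.

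**The plan's figure, n = 23.** SE = 7 × √(2/23) = 2.064 and λ = 5.75 / 2.064 = 2.786. Normal approximation: Φ(2.786 − 1.960) = Φ(0.826) = 79.5%, which rounds to the stated 80%.

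**The named test, difference 5.75, SD 7:**

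| Completers per group | λ | t critical value | t-test power | Normal approximation |
|---|---|---|---|---|
| 22.5 | 2.755 | 2.017 | 76.8% | 78.7% |
| 23 | 2.786 | 2.015 | 77.8% | 79.5% |
| 25 | 2.904 | 2.011 | 81.2% | 82.8% |

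Sidedness does not explain the 80%: a one-sided t-test at 23 per group would give 86.4%.

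**Difference detectable with 80% power (t-test).** 5.91 at 23 per group and 5.98 at 22.5, against the stated 5.75.

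**Completers needed for 80% at 5.75 (t-test).** The solution is 24.3, so 25 per group. At 25% dropout that is 25 / 0.75 = 33.3, or 34 enrolled per group.

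**The current 90.** The documents give no allocation ratio for the 90; 1:1 (45 per arm) is assumed here.
- If half provide a 3-month MIDAS: 45 × 0.5 = 22.5 per arm, power 76.8%.
- If MIDAS dropout stays at 25%: 45 × 0.75 = 33.75 per arm, λ = 3.374, power 91.4%.
- For comparison, the initial 30 per group at half follow-through: 15 per arm, λ = 2.250, power 58.4%.

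**Sensitivity to the SD, t-test, 23 per group.** SD 5: 96.8%. SD 6: 88.8%. SD 6.8: 80.1%. SD 7: 77.8%.

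**The case against.** The case for leaving the text alone has real force. The plan says approximately 23, a standard formula gives 79.5% there, and the shortfall under the t-test is only 2.2 points. The SD matters far more: the plan took the top of its own range, and an SD of 6.8 instead of 7 would bring the t-test to 80%. The statement describes the initial plan, nothing claims 80% for the 90, the size was justified on PMR compliance, and Aim 2 hypothesises only trends. All of this stands, and it makes the point minor. It does not make the sentence correct, because the 80% is attached to SD 7 and to a t-test.

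A reader might go further and infer that the move to 90 merely restores the same shortfall, so that the plan is wrong to call it more adequate. The documents do not support that. The inference treats full follow-through as meaning a completed 3-month MIDAS, but the phrase is undefined and could refer to PMR or diary use. Under Methods & Procedures, MIDAS is collected by phone or email, with a call to those who do not complete it electronically, and subjects who withdraw are asked to complete it first. MIDAS completion could therefore be better than half. Even at half, 90 gives about 77% where the initial 60 would have given about 58%, so 90 is indeed more adequate.

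A reader might also quote 76%, which corresponds to 22 completers per arm (75.9%). The plan states 23, and its own arithmetic gives 22.5; 22 appears nowhere.

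**Conclusion.** The point holds as a minor error in a stated figure. For the plan's own SD, difference, alpha and test, power is 77.8% at 23 per group and 76.8% at 22.5, not 80%. The difference detectable with 80% power is about 5.9 to 6.0. The source of the 80% is not documented, but the normal approximation accounts for it.

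Separately, the plan gives no power for its current Phase 2 number. Under 1:1 allocation and SD 7 the range is about 77% to 91%, depending on whether MIDAS completion is one half or three quarters. Both the allocation and the completion rates are assumptions for the 90. The feasibility aim, on which the trial was sized, is unaffected.

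**What to change.** In the Phase 2 sample-size text:

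1. Restate the initial figure as about 78% power for a difference of 5.75, or 80% power for a difference of about 5.9, with 23 completers per group, SD 7 and the two-sided t-test at 0.05.
2. Add the power for 90 randomised. State the allocation ratio, say what full follow-through means, and give the assumed proportion with a 3-month MIDAS. If that proportion is uncertain, give the range: about 77% at one half and about 91% at three quarters, under 1:1 allocation.

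This costs two or three sentences and a slightly lower stated power for the initial plan. It needs no change to the design, the number of subjects or the analysis.

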be the same as before but instead of coming for an in-person appointment, subjects will enroll via virtual sessions. Like before, the data is stored and can be viewed by the PI and study team online. In this iteration, subjects may contact the physician/the physician may contact the subject to discuss app data if s/he wants to discuss headache management as part of clinical care. This is intended to take the place of paper diaries which were used during in-office visits.

Phase 2 of the study will be a two-arm randomized controlled trial (RCT) in the outpatient setting at NYULMC to assess feasibility and acceptability of the RELAX approach. The duration of Phase 2 is 3 months. We are beginning the urgent care RCT in May 2019. All patients will complete a migraine disability and migraine quality of life assessment and track their headache frequency and intensity using our RELAXaHEAD app. Data will be collected from the app and adherence will be reinforced with blinded telephone calls. Data collection on these outcomes are important to determine the user burden of data collection. The subjects will only use the application for an initial 60days based on the data we have to date (from Phase 1), and we will see if subjects continue to use the application during the third month.

The physician / NTV will provide the open-enrollment card to potential subjects when they approach them about the study.

Designated study team members will pre-screen patients in Epic as indicated elsewhere in the procedure using the Epic Research Report. They will obtain patient consent for the study. Once consented, patients will be randomized to RELAX or MUC. The study team member will then collect patients' health histories and baseline data in REDCap on an iPad, download the app onto patients' smartphones, and conduct the sessions (see below). Physicians listed as study staff on this protocol may also consent and enroll eligible patients if they note that one of the patients under his/her care is appropriate for the study. There is currently an Android version and an IOS version. In addition, we will use Data Core to locate potentially eligible patients with migraine within the NYU health system at NYU Langone and NYU Brooklyn sites from primary care and the various neurology divisions. These potential patients will be sent a message via MyChart.

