- 1. Please remember to use the app.
- 2. Hi, The RELAXaHEAD team is trying to reach you. Please call xxx-yyy-zzz [study phone number]?
- 3. You are due for your follow-up call/email. Please be sure to call us at xx-yyy-zzzz or respond to the email. The RELAXaHEAD team.

- 4. Remember-relaxation is beneficial for your health.
- 5. The best way to add relaxation into your routine is to pair it with an activity you do each day. Let us know if you want to discuss how to improve your adherence with the RELAXaHEAD app.
- 6. Research has suggested that the more one is able to practice relaxation, the better one's health. Log into the RELAXaHEAD app when able.
 - 7. We will text participants once a week from our NYU MCIT study phone confirming that we have recorded that they have spent x amount of time practicing PMR within the application, and asking if they have practiced PMR independently without the application that week.

Follow-up will be assured by testing the subject's phone number in front of the subject and asking for alternative contact information. Subjects will also be called/emailed.texted after 3 days of no daily diary entry. If they are not reached, an email via [contact] will also be sent as a reminder to input the data. During the calls, a designated study team member will reiterate the importance of adherence with the app. At 1,2 and 3 months, subjects will be asked to complete the MSQv2 and the MIDAS via phone or email to assess the treatment benefits. A designated study member will call the patient if they do not complete the assessment electronically. Throughout the study, subjects will be asked to record electronically any new and/or discontinued medications and interactions with the medical community. The study team also wants to collect additional patient information such as medications used before and after the research study (especially opioids), healthcare utilization, and comorbid diagnoses via i2b2, a member-driven non-profit foundation developing an open-source / open-data informatics community.

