The following questionnaires: PROMIS depression and anxiety screens, Insomnia Sleep Index (ISI) and the Perceived Stress Scale will be administered via REDCap.

In addition to the application, REDCap, a HIPAA Compliant research database system will be used. The study identifier and the PHI of the subjects will be stored in REDCap. In addition, we will use REDCap to send out the MIDAS to the subjects.

We will use the REDCap randomization feature to randomize our subjects.

DataAnalysis and DataMonitoring Analysis Plan

Table 2 describes the outcome measures that will be used. We considered the feasibility outcome measures recommended by Kraemer and colleagues for pilot studies.³¹ For this study, feasibility will be operationally defined as study recruitment, retention, and adherence measures for doing the PMR. Acceptability will be operationally defined as attrition, satisfaction, and willingness to participate in a similar intervention in the future. Satisfaction questions are as follows:

Responses will be 0-5 on the Likert Scale:

Daily Diary Satisfaction Questions

- 1. The app was easy to use
- 2. The information was easy to understand
- 3. The daily diary was relevant to me to help track my headaches
- 4. The app kept my interest and attention
- 5. I would be happy to use the app again

PMR Satisfaction Questions

- 1. The relaxation kept my interest and attention
- 2. The relaxation helped to improve my stress and low mood
- 3. The relaxation taught me skills that will help me handle future problems
- 4. I would be happy to do the relaxation again

Our primary outcome will be the change in the MSQv2 -a validated migraine quality of life measure (https://eprovide.mapi-trust.org/instruments/migraine-specific-quality-of-life-questionnaire). We will also use the Migraine Disability Assessment Scale (MIDAS), measures disability over the past 3 months. 32-35 MIDAS scores have been shown to have excellent test-retest reliability, high internal consistency, and high external validity using a variety of measures—including diary-based measures. 32,34 MIDAS scores are also positively associated with physician judgements about the severity of headache and the need for treatment. 33 In the MS- migraine patient population, we will also assess the MOS Pain Effects Scale (PES).

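### Phase 2 collects baseline questionnaires after randomisation with no masking described at T0, and the diary-based 50% decrease has no pre-treatment diary reference

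*Combined protocol and SAP*

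**What the plan says.** **Order of steps.** In the Phase 2 text of Methods & Procedures: "Once consented, patients will be randomized to RELAX or MUC. The study team member will then collect" the patients' "health histories and baseline data in REDCap on an iPad, download the app onto" their phones, and conduct the session. The same team role collects the baseline and runs the session. The only Phase 2 procedure called blinded is the follow-up contact: "adherence will be reinforced with blinded telephone calls". The visit schedule names a baseline assessment, T0, without saying who knows the arm at that point.

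**Outcomes that use T0.** The Analysis Plan states: "Our primary outcome will be the change in the MSQv2". Table 2 instead gives as primary the "difference between scores of MIDAS" at 3 months and baseline. The timed assessments are given as: "At 1,2 and 3 months, subjects will be asked to complete the MSQv2 and the MIDAS". No time is given for a baseline MSQv2. PROMIS, ISI and the Perceived Stress Scale are to be given through REDCap, also without a stated time.

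**Information needed for entry.** The Inclusion Criteria list "Migraine Disability Assessment (MIDAS) score >5" and at least 4 headache days a month, with an ISI of 15 or more also listed. The recruitment section places the MIDAS and headache-day criteria at pre-screening. Nothing says whether these values are the analysis baseline.

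**Diary.** The Symptoms Diary section makes the diary available only through the app. RELAX patients do PMR at the enrolment session, and week 1 of the Intervention list is already programme content. Table 2 defines the pain outcome as "50% decrease in frequency and/or intensity of HAs (measured by electronic HA diary data"), with frequency counted per 30 days and no reference period named.

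**The concern.** A baseline should be fixed before anyone can react to the allocation. Here the stated order puts it afterwards, for outcomes that are entirely patient-reported. Under Subject/Representative Comprehension, patients must show they understand that the additional intervention is offered at random. They therefore know the contrast, and learning the arm could colour their answers. The person collecting the answers also has to know the arm by the time the app is loaded, because the MUC version has PMR blocked.

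A change score is follow-up minus baseline, so an arm-dependent shift at T0 passes into it in full, in either direction. This applies to a within-arm change as well as to a between-arm comparison. The Aim 1 adherence and satisfaction outcomes are not affected.

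The diary problem is different and needs no assumption about bias. A percentage decrease needs a starting value, and the plan provides no diary days before treatment. If early diary days were used instead, part of any effect would already be in the reference.

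**Working it through.** **1. What is exposed, instrument by instrument**

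| Instrument | Value required before randomisation? | Exposure |
|---|---|---|
| MSQv2 | None stated; timed only at 1, 2 and 3 months | Firm, if baseline is taken where the plan puts baseline data |
| PROMIS, Perceived Stress Scale | None stated | Same |
| MIDAS, headache days, ISI | Yes, as entry criteria | Only if a post-randomisation value is used as baseline |

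The Phase 2 text also says that all patients complete disability and quality-of-life assessments, without a time. That leaves a second, T0 MIDAS possible but not stated.

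**2. The plan's own power figure**

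Inputs from the Phase 2 sample-size text: SD of MIDAS change 7, difference 5.75, 30 × 0.75 = 22.5 or about 23 per group, two-sided 5% two-sample t-test, 80% power.

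- Standard error = 7 × √(2/23) = 7 × 0.2949 = 2.064; 5.75/2.064 = 2.786.
- Normal approximation: Φ(2.786 − 1.96) = 79.5%, which reproduces the stated 80%. The exact t-test gives 77.8%.

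This figure is not in dispute. It shows that a between-arm test on change was contemplated and supplies the SD and group size used below.

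**3. Illustration of a T0 shift**

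Assumptions: no true effect, and a between-arm shift at T0 whose size is assumed because the documents give none. Noncentrality = (shift/SD)/√(2/n), with 44 degrees of freedom and critical value 2.015 at n = 23. Example: 2 MIDAS points at SD 7 gives (2/7)/0.2949 = 0.969, hence a 15.8% rejection rate.

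| Shift | False-positive rate, n = 23 |
|---|---|
| MSQv2: 0.05 / 0.1 / 0.2 / 0.3 SD of change | 5.3 / 6.3 / 10.2 / 16.9% |
| MIDAS: 0.5 / 1 / 2 / 3 points, SD 7, only if T0 is the baseline | 5.6 / 7.6 / 15.8 / 29.6% |

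The plan also reports that about half of patients follow through fully: 90 × 0.5 = 45, or 22 to 23 per group. At 22 the MIDAS row becomes 5.6 / 7.5 / 15.3 / 28.4%. Doubling the 5% rate takes 0.197 SD at n = 23: 7 × 0.197 = 1.38 points, or 5 × 0.197 = 0.98 points at the plan's lower SD of 5. A shift of half a point or less matters little.

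**4. Diary reference**

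The stated sequence is randomisation, app installed, diary begins, intervention from the first session. No diary day precedes treatment.

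Suppose the first 30 diary days were the reference and already held a fraction f of the final reduction e. The measured reduction is then 1 − (1 − e)/(1 − f·e).

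- For e = 50% and f = 0.25: 1 − 0.5/0.875 = 42.9%.
- For e = 50% and f = 0.5: 1 − 0.5/0.75 = 33.3%.
- The true reduction needed to register as 50% is 0.5/(1 − 0.5f): 57.1% and 66.7%.

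The values of f are assumed.

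**5. Precision of an analysis without T0**

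With equal variances, the standard error of a follow-up-only comparison relative to the change score is √(1/(2(1 − ρ))). At an assumed baseline-to-follow-up correlation ρ of 0.3, 0.5 or 0.7 this is 0.85, 1.00 or 1.29.

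**The case against.** **Patients may not know their arm at T0.** Baseline collection is listed before the app download and the session, and the arm-specific explanations belong to that session. This stands. A reader might infer that T0 is unmasked, or that treatment has begun; the text supports neither. It supports only that the order is wrong way round and that no protection is described.

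**MIDAS is known at screening.** This largely stands. A reader might infer that the powered MIDAS comparison carries a false-positive rate of 15.8% or 29.6%. It does not follow. Those figures need both a post-randomisation MIDAS baseline and an assumed shift of 2 or 3 points, and the documents establish neither.

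**The silence on a baseline MSQv2 cuts both ways.** It stands in part: the Phase 2 text does not list the instruments within baseline data. But a change in MSQv2 needs a baseline, and the only place the plan puts baseline data is after randomisation.

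**Aim 2 is exploratory.** This stands. The Purpose section describes analyses within group and speaks of trends. Even so, these outcomes are labelled primary, and the sample-size text powers a between-arm t-test on MIDAS change, so that comparison is likely to be read.

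**Reordering does not cure an open trial.** This stands. No participant masking is described, so self-report at 1 to 3 months stays open to reporting bias. Reordering also repairs nothing for patients already randomised; the urgent care trial was to begin in May 2019 and the document is dated July 2022.

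**Week 1 is deep breathing, and the enrolment PMR is described in an ED although Phase 2 is outpatient.** Even setting the ED sentence aside, week 1 is listed as intervention and the app is installed only after randomisation.

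**Conclusion.** The concern holds in two limited parts.

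First, baseline data are collected after randomisation, by the role that also delivers the arm-specific session, with no masking described at T0. Bias is possible, not shown, and its size and direction are unknown. The point is firmest for MSQv2, PROMIS and the Perceived Stress Scale, and conditional for MIDAS, ISI and headache days. The false-positive figures are illustrations on assumed shifts and should not be quoted as properties of this trial. The case for acting rests on the correction being almost free.

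Second, the secondary diary-measured 50% decrease cannot be calculated against a pre-treatment diary value as the plan stands. This rests on the stated sequence alone. How far using early diary days would dilute an effect depends on an assumed fraction.

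One might read this as undermining the trial as a whole. It does not: the feasibility aim is untouched, and Aim 2 is exploratory.

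**What to change.** **T0 questionnaires**

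- For all further patients, use the order: consent; eligibility check and every T0 questionnaire (MIDAS, MSQv2, PROMIS, ISI, Perceived Stress Scale, and an exact past-month headache-day count); REDCap randomisation; app download and session.
- State that the pre-randomisation MIDAS is the baseline.
- For patients already randomised, record which order each followed. Add a sensitivity analysis comparing 3-month scores between arms without T0, adjusting MIDAS for the screening value if it was recorded. This removes a T0 shift but not reporting bias at follow-up.

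**Diary outcome**

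- Compare arms on diary headache days per 30 days and, separately, on diary intensity, in a stated follow-up window. Adjust frequency for the pre-randomisation headache-day count, and intensity for a pre-randomisation rating if one is collected at T0.
- Do not report the 50% responder outcome as a change from a diary baseline.
- Before fixing the window, reconcile the 60-day app-use period in Methods & Procedures with the 12-week adherence definition and 3-month hypothesis in the Purpose section.

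**Cost.** The reordering stays within the same visit and needs no new visits or staff. The diary change needs revised outcome wording, one exact count and, optionally, one intensity rating. The sensitivity analysis needs no new data, though it loses precision if baseline and follow-up correlate strongly (standard error ratio 1.29 at ρ = 0.7). The drawbacks are that the headache baseline is recalled rather than diary-based, and that T0 differs in kind between earlier and later patients. A diary run-in on the existing PMR-blocked app would give a true diary baseline, but it would delay randomisation by its full length, so it is the costlier option.
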